Table 2: Study Activities for Study 109MS310 - Table 2 of 2

Tests and Assessments	[REDACTED]	Discontinuation and/or Withdrawal Visit ²	Lymphocyte Follow-Up Visit ³	Unscheduled Visit for Abnormal Laboratory Results (Other Than Lymphocytes)
		These visits can be combined. If these visits are not combined, any assessment that was performed within the past 2 weeks (or the interval noted in the footnotes) does not need to be repeated unless clinically indicated.		
Physical Examination ⁴	X		X	
Vital Signs ⁵	X	X	X	
Hematology (CBC With Differential)	X	X	X	X ⁶
Blood Chemistry	X	X		X ⁷
[REDACTED]				
Lymphocyte Subset Analysis		X	X	
[REDACTED]				
Concomitant Therapy and Procedures		X		
AE Recording		X		
SAE Recording	Monitor and record throughout the study.			

AE = adverse event; ALT = alanine transaminase; AST = aspartate transaminase; CBC = complete blood count; [REDACTED]; LLN = lower limit of normal; [REDACTED]; SAE = serious adverse event; ULN = upper limit of normal; WBC = white blood cell.

² Discontinuation refers to discontinuation of study treatment. Withdrawal refers to withdrawal of subjects from study. The Discontinuation and/or Withdrawal Visit should be conducted as soon as possible and no later than 2 weeks after their last dose of study treatment.

CONFIDENTIAL

The information contained herein may not be used, disclosed, or published without the written consent of Biogen MA Inc.

³ Subjects who complete, temporarily withhold, or permanently discontinue study treatment for any reason and have a lymphocyte count <LLN will continue protocol-required visits and assessments and will also be followed up every 4 weeks for 24 weeks, then every 12 weeks (**unless clinically indicated more often or at the Investigator's discretion**) until the lymphocyte count is \geq LLN or for up to 48 weeks following drug discontinuation, whichever occurs sooner.

⁴ Physical examination includes height and weight measurements, as well as a neurological examination.

⁵ Vital signs will include diastolic and systolic blood pressure, heart rate, and temperature. Subjects must be seated for 5 minutes prior to having their pulse and blood pressure measured.

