5.2.5 Time on Study and Treatment

The total number of days/weeks patients on study will be summarized. Number of weeks the subject on the study will also be categorized into 12 week intervals and summarized. The total number of days subjects on study is calculated as

$$\text{Date of study end} - \text{date of first dose} + 1.$$

The total number of days/weeks patients on treatment will be summarized. Number of weeks the subject on treatment will also be categorized into 12 week intervals and summarized.

The time patients on temporary drug interruption will be excluded from the time on treatment calculation. Therefore, the total number of days subjects on treatment is calculated as

$$(\text{Date of last dose} - \text{date of first dose} + 1) - \text{total days of temporary dose interruption if any.}$$

For partial study or study treatment end date, if day is missing then impute the day to 30/31/28/29 depending on the month; if day and month are missing then impute the month and day to December 31st.

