5.2.7 Concomitant Medications and Non-drug Therapies

Concomitant medication is defined as prescribed or over-the-counter medications used during the study (e.g., either started prior to the study and continued on the study or started on or after the first dose of study drug). If a medication had a missing start date and a missing end date, or had a missing start date and an end date which was after the first day the subject was on study drug, or a start date which was after the date of the first day the subject was on study drug, the medication is considered concomitant. When partial concomitant medication start or end date exists, before determining whether concomitant or not, the following imputation rules are applied.

Partial start dates:

If day is missing (only month and year are present)

- If year and month are same as treatment start date then assign the day of treatment start date to the partial date
- Otherwise assign the day to '01'

If only year is present

- If year is same as treatment start date then assign the month and day of the treatment start date to the partial date
- Otherwise assign the month and day to 'January-01'

Partial end dates:

If day is missing (only month and year are present)

- If year and month are same as the year and month of study end date then assign the day of the study end date to the partial date
- If year and month are prior to the year and month of study end date then assign the last day of the month (28, 29, 30 or 31)

If only year is present

- If year is same as the year of study end date then assign the month and day of the study end date to the partial date
- If year is prior to the year of study end date then assign 'December-31' to the partial date.

If the study is ongoing and study end date is not available then the cut-off date will be used in the place of study end date

The WHO dictionary will be used for coding concomitant medication. MedDRA is used for coding concomitant non-drug therapies.

CONFIDENTIAL

The information contained herein may not be used, disclosed, or published without the written consent of
 Biogen Idec MA Inc.

	Protocol 109MS310 An Open-Label Study to Assess the Effects of BG00012 on Lymphocyte Subsets in Subjects With RRMS	Final Version 1.0
---	---	--------------------------

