5.3.3 Lymphocyte analysis during lymphocyte follow-up period

Subjects who temporarily withhold, or permanently discontinue study treatment for any reason and have a lymphocyte count <LLN will continue protocol-required visits and assessments and will also be followed up every 4 weeks for 24 weeks, then every 12 weeks (unless clinically indicated more often or at the Investigator's discretion) until the lymphocyte count is \geq LLN or for up to 48 weeks following drug discontinuation, whichever occurs sooner.

In general, the lymphocyte follow-up analysis will include subjects who have at least one ALC < LLN during the treatment period and have at least one ALC value during the lymphocyte follow-up period. The lymphocyte follow-up period is defined as the time starting from the date of temporary dose interruption or study drug discontinuation. The start date of the lymphocyte follow-up period is defined as the start date of temporary dose interruption or the treatment end date. The last observed value collected on or prior to the date of temporary dose interruption or study drug discontinuation will be the reference point (lymphocyte follow-up baseline). Data that are collected during the lymphocyte follow-up period will be assigned to an appropriate visit by using the mid-point of the two visits windowing scheme. Visits will be mapped every 4 weeks for 24 weeks and then every 12 weeks afterward. The detailed windowing rule is available in [Appendix 2](#). Patients who have any post lymphocyte follow-up baseline values will be included in the analysis. ALCs collected during the lymphocyte follow-up period will be analyzed. The lymphocyte subsets and Ig isotypes observed obvious decline over time in the treatment period will also be explored.

The by-visit summary of actual value, change and percent change from the lymphocyte follow-up baseline in ALC during the lymphocyte follow-up period will be presented. The by-visit summary of actual value, change and percent change from the study baseline in ALC during the whole study period will also be presented. In addition, graphical display of median (Q1/Q3) of actual value in ALC in the whole study period will be presented; graphical display of median (Q1/Q3) of percent change from study baseline and lymphocyte follow-up baseline will be presented. The same analyses will be applied to selected lymphocyte subsets and Ig isotypes of interest.

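### SAP 5.2.5 imputes a partial treatment or study end date to month-end or 31 December without an upper limit, so exposure can run past the subject's own study end

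*SAP*

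**What the plan says.** SAP 5.2.5 gives one rule for incomplete end dates: "For partial study or study treatment end date, if day is missing then impute the day to 30/31/28/29 depending on the month". For a date with only the year, it continues "if day and month are missing then impute the month and day to December 31st". Nothing bounds the result by study end, a visit, death or a data cut-off. The same section computes time on treatment from the last-dose date, and time on study from the study end date.

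The SAP treats other partial end dates differently. For concomitant medications (5.2.7) it says "If year and month are same as the year and month of study end date then assign the day of the study end date", and for a year-only date in the year of study end, "then assign the month and day of the study end date to the partial date". If the study is ongoing, the cut-off date replaces study end. SAP 5.4.1 repeats these rules for adverse events.

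The treatment end date appears again in SAP 5.3.3: "The start date of the lymphocyte follow-up period is defined as the start date of temporary dose interruption or the treatment end date". The follow-up baseline is fixed by the same event: "The last observed value collected on or prior to the date of temporary dose interruption or study drug discontinuation will be the reference point". Appendix 2 puts any value up to and including the follow-up start date in the baseline window.

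**The concern.** The rule always picks the latest date compatible with what was recorded, so errors all go one way and do not cancel. Without a cap, a subject can be credited with drug after the final visit, and even beyond the planned maximum participation. The SAP already has the cap it needs and applies it to everything except the study drug and study end. A partial study end date is also imputed without a cap, and that date then serves as the bound for adverse events and medications.

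Exposure and compliance (5.2.5 and 5.2.6) are affected directly. The lymphocyte follow-up summaries (5.3.3) are affected if they use the imputed date: samples taken after the drug was stopped would then count as taken on or before stopping, and later samples would be given visit labels that are too early.

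**Working it through.** The plan states no figure to reproduce, so this is calendar arithmetic on its own rules.

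**Inputs**
- Imputation rule and exposure formula, last dose − first dose + 1 − interruption days: SAP 5.2.5.
- Expected capsules, 4 a day except 2 a day in week 1, so 4 × days − 14; capsules taken = expected − missed: SAP 5.2.6.
- Discontinuation/Withdrawal Visit "should be conducted as soon as possible and no later than 2 weeks after their last dose of study treatment", that is 0 to 14 days after stopping, with hematology and lymphocyte subsets: Protocol 4.2, Table 2.
- Final Follow-Up Visit 28 days after last dose, ±5 days: Protocol 4.2, Table 1.
- Lymphocyte follow-up at weeks 4, 8, 12, 16, 20, 24, 36 and 48: SAP 5.3.3 and Appendix 2.
- Participation up to 104 weeks: SAP 2.2.
- Assumptions: the true last-dose date is uniform over a 365-day year, and visits fall on their target days. Dates in the examples are illustrative.

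**1. Size of the shift.** In a month of L days, a true date on day d moves L − d days later.

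| | Day missing | Year only |
|---|---|---|
| Range | 0 to 30 days | 0 to 364 days |
| Mean | (7×465 + 4×435 + 378)/365 = 14.7 | 364/2 = 182 |
| Shift ≥ 14 days | (7×17 + 4×16 + 14)/365 = 54% | 351/365 = 96% |
| Shift ≥ 28 days | (7×3 + 4×2 + 0)/365 = 8% | 337/365 = 92% |
| Shift ≥ 168 days | none | 197/365 = 54% |

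With the day missing, the overrun past a Follow-Up Visit on Day +28 is at most 30 − 28 = 2 days, or 30 − 23 = 7 days if that visit is held 5 days early. The year-only case is the large one.

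**2. Exposure.** Take first dose 2 June 2015, true last dose 3 March 2016 and no interruption; true exposure is 276 days.
- Day missing: imputed 31 March 2016, exposure 304 days, excess 28.
- Year only: imputed 31 December 2016, exposure 579 days, excess 303. That is 275 days after a final visit on 31 March 2016.
- A 96-week completer (1 April 2015 to 31 January 2017, 672 days) with only the year recorded is credited with 1006 days, or 143.7 weeks, against 96 weeks of treatment and 104 weeks of participation.

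**3. Compliance.** Same subject, with 25% of capsules truly missed. Expected = 4×276 − 14 = 1090, missed = 272.5, compliance 75.0%.
- Day missing: expected 4×304 − 14 = 1202; (1202 − 272.5)/1202 = 77.3%.
- Year only: expected 4×579 − 14 = 2302; (2302 − 272.5)/2302 = 88.2%.

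Numerator and denominator both grow, which limits the change when only the day is missing.

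**4. Lymphocyte follow-up, if 5.3.3 takes the imputed date.**
- True stop 3 March, day missing: the 4-week off-drug sample (31 March) is on the imputed date and becomes the baseline. The 8-week sample (28 April) is Day 29 from 31 March, so Appendix 2 (Day 2 to 42) labels it 4 weeks.
- True stop 15 March, discontinuation visit 10 days later (25 March), day missing: that visit precedes 31 March and becomes the baseline, 10 days off drug.
- True stop 3 March, year only, follow-up continuing: the 36-week sample (10 November 2016) becomes the baseline.

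**5. What a cap does.** For the 3 March stop with a discontinuation visit on 13 March, a study-end cap (31 March) leaves an excess of 28 days, and a cap at the discontinuation visit leaves 10. Under either cap an off-drug sample still lies on or before the capped date, so the baseline needs its own condition.

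**The case against.** The strongest reply is that SAP 5.3.3 never invokes the 5.2.5 rule. That rule sits beside the duration formulas, and SAP 5.1 says in general that missing data are not imputed. This stands in part: use of the imputed date in 5.3.3 is an inference. But 5.3.3 names the treatment end date, and the SAP offers no other way to complete it.

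Partial dates should also be rare. Dosing goes on the dosing CRF (Protocol 15.4.2), capsules are counted at visits (11.5), supply is accounted for by subject (12.1.4), monitors resolve omissions (18.3), and the discontinuation and follow-up visits are both timed from the last dose. A year-only date is hard to square with all this. That stands, and it limits the expected effect on any summary.

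The 3 March example is near the worst case for a missing day: only about 8% of such dates reach the 4-week sample.

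A reader might go further and infer that recovery is understated. The documents do not support that as a finding. They give no off-drug recovery rate, so the change in count at a mis-assigned sample is unknown. SAP 5.3.3 also reports actual values and change from study baseline, neither of which uses the follow-up baseline value.

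None of these arguments supplies the missing cap in 5.2.5.

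**Conclusion.** The point holds, as a minor one. Followed as written, SAP 5.2.5 overstates time on treatment for each subject with a partial end date, by 0 to 30 days (mean about 15) or 0 to 364 days (mean about 182), and can place the last dose after study end. The means assume a uniform true date; the direction does not. In the example, compliance rises from 75.0% to 77.3% or 88.2%.

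The effect on the lymphocyte follow-up baseline is conditional on 5.3.3 using the imputed date. It concerns permanent discontinuation or completion only, because the 5.2.5 rule does not cover the start of a temporary interruption.

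A reader might infer that the main results are at risk. They are not: the primary Week 48 analysis uses change from study baseline in visit windows counted from first dose (SAP 5.1 and Appendix 2). What is exposed is descriptive: exposure, compliance and the follow-up summaries, for an unstated and probably small number of subjects.

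**What to change.** - **SAP 5.2.5, treatment end date.** Use the earliest of: the imputed date; the Discontinuation/Withdrawal Visit or other first contact documenting that drug has stopped; study end; death; data cut-off.
- **SAP 5.2.5, study end date.** Cap a partial date at last contact or cut-off.
- **SAP 5.2.6.** Use the capped treatment end date for expected capsules.
- **SAP 5.3.3.** State how a partial end date is handled. For subjects with an imputed end date, require the follow-up baseline to be the last sample taken before any visit documented as off-drug. The cap alone is not enough, because the discontinuation visit may itself be up to 14 days off drug and includes blood sampling.

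The cost is a few lines of SAP text, a minimum over dates in the derivation and one condition on baseline selection. No new data are needed, and nothing changes for sites or subjects.

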5.2.6 Treatment Compliance

The total number of study drug capsules taken by the subject will be summarized. The compliance through the date of last dose of study drug and the overall 96-week compliance who complete the study will be summarized. The percent compliance is defined as follows for each subject:

$$\text{Percent Compliance} = [(\text{total number of capsules taken}) / (\text{total number of capsules subject is expected to take})] *100$$

The total number of capsules that the subject expected to take is defined as the number of days the subject on the study drug multiplied by 4 (4 capsules is the expected number per day), except for the first week where 2 capsules a day is expected. The total number of capsules actually taken is calculated using total number of doses expected minus the missed doses.

CONFIDENTIAL

The information contained herein may not be used, disclosed, or published without the written consent of Biogen Idec MA Inc.

	Protocol 109MS310 An Open-Label Study to Assess the Effects of BG00012 on Lymphocyte Subsets in Subjects With RRMS	Final Version 1.0
---	---	--------------------------

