11. STUDY TREATMENT USE

11.1. Regimen

Refer to and follow the Directions for Handling and Administration (DHA).

BG00012 will be taken orally at a dose of 120 mg BID for the first 7 days and at a maintenance dose of 240 mg BID thereafter. Temporary dose reductions to 120 mg BID may be considered for individuals who do not tolerate the maintenance dose due to flushing and/or GI disturbances. Within 4 weeks, the recommended dose of 240 mg BID should be resumed. Subjects will receive treatment for 96 weeks.

Missed doses should be taken within 6 hours. If the subject does not remember to take the dose within 6 hours, this dose should be skipped, and the next dose should be taken as scheduled. Doses should not be doubled to make up for missed doses.

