11.2.4. Dosage Reductions

Dosage reduction will be allowed only for subjects who are unable to tolerate study treatment due to flushing and/or GI disturbances (dosage reductions will not be allowed for abnormal laboratory values; for management of abnormal laboratory values, refer to Sections [11.2.1](#), [11.2.2](#), and [11.2.3](#)). Subjects who do not tolerate study treatment will reduce their dosage by taking 120 mg BID for up to 4 weeks. Within 4 weeks at the reduced dosage, subjects will resume taking the full dose of 240 mg BID. If the subject is still unable to tolerate study treatment, the subject must discontinue study treatment as described in Section [10.1](#). Subjects who do not tolerate study treatment will complete the final Follow-Up Visit 4 weeks after their last dose of study treatment and will then be withdrawn from the study (Section [10](#)).

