11.5. Compliance

Compliance with treatment dosing is to be monitored and recorded by site staff. Compliance will be monitored by capsule count conducted by study personnel at protocol-scheduled visits.

CONFIDENTIAL

The information contained herein may not be used, disclosed, or published without the written consent of Biogen MA Inc.

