12.1. BG00012

BG00012 is a drug product formulated as enteric-coated microtablets in gelatin capsules (blue and white) for oral administration. Each capsule contains 120 mg BG00012.

Excipients for the manufacturing of the enteric-coated microtablets include microcrystalline cellulose, croscarmellose sodium, talc, colloidal anhydrous silica (colloidal silicon dioxide), magnesium stearate, triethyl citrate, methacrylic acid-methyl methacrylate copolymer, methacrylic acid-ethyl acrylate copolymer, simethicone, sodium lauryl sulfate, and polysorbate 80. Excipients for the manufacturing of the capsule shell include gelatin, titanium dioxide, and indigotin.

The contents of the study treatment label will be in accordance with all applicable regulatory requirements. Do not use study treatment after the expiration date unless a written notification of an expiration date extension is provided by Biogen.

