2.2 Overall Study Duration and Follow-Up

The study period will consist of a Screening Visit within 4 weeks of Baseline, a Treatment Period of 96 weeks and a final Follow-Up Visit. Subjects will receive treatment for 96 weeks. The total duration of subject participation will be up to 104 weeks.

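### SAP 5.2.6 derives capsules taken from a count of doses without converting doses to capsules; read literally, a fully compliant 96-week subject scores 50.3%

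*SAP*

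**What the plan says.** SAP 5.2.6 (Treatment Compliance) promises two outputs: the total number of capsules each subject took, and percent compliance, displayed as capsules taken divided by capsules expected, times 100.

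The denominator is in capsules. It is days on study drug times 4 ("4 capsules is the expected number per day"), with 2 per day in the first week as the only exception.

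The numerator is then derived as follows: "The total number of capsules actually taken is calculated using total number of doses expected minus the missed doses". The section does not define expected doses, does not say where missed doses are recorded, and gives no factor from doses to capsules.

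The protocol shows that the two units differ. Section 11.1 gives treatment "at a dose of 120 mg BID for the first 7 days and at a maintenance dose of 240 mg BID thereafter", and Section 12.1 says "Each capsule contains 120 mg BG00012". One dose is therefore one capsule in week 1 and two capsules at maintenance. Section 11.1 also uses the word dose for a single twice-daily administration, in its rules for late and missed doses.

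On data source, Protocol 11.5 says: "Compliance will be monitored by capsule count conducted by study personnel at protocol-scheduled visits".

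**The concern.** The displayed ratio is sound, but the sentence that fills its numerator counts in a unit that is half the size of the denominator's after week 1. A programmer who follows the text exactly divides doses by capsules. A programmer who notices the mismatch may repair only the first term and subtract a count of missed doses from expected capsules. The first error is large and would probably be noticed. The second gives plausible figures and may not be.

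This is a single-arm study of a drug effect on lymphocytes, so readers will use the compliance table to judge whether the observed changes reflect drug actually taken. A figure that is halved, or that hides half of the missed intake, misinforms that judgement.

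**Working it through.** The documents give no compliance value for a fully compliant subject, so there is no stated figure to reproduce.

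**Inputs**
- Duration: 96 weeks = 672 days (SAP 2.2: "Subjects will receive treatment for 96 weeks").
- Doses per day: 2 throughout (Protocol 11.1).
- Capsules per dose: 1 on days 1 to 7, 2 afterwards (Protocol 11.1 and 12.1).
- Capsules expected per day: 2 in week 1, 4 afterwards (SAP 5.2.6).

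**Totals over 672 days**
- Capsules expected: 7 × 2 + 665 × 4 = 14 + 2660 = 2674.
- Doses expected: 672 × 2 = 1344.
- 20% of doses missed: 0.2 × 1344 = 268.8 doses.

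**Three ways to program the numerator**

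| Reading | Numerator | No dose missed | 20% of doses missed |
|---|---|---|---|
| Literal | doses expected − doses missed | 1344/2674 = 50.3% | (1344 − 268.8)/2674 = 40.2% |
| Mixed | capsules expected − doses missed | 2674/2674 = 100% | (2674 − 268.8)/2674 = 89.9% |
| Loose | capsules expected − capsules missed | 2674/2674 = 100% | 80% |

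The correct value with 20% of doses missed is 80% if the misses are spread evenly, and (2674 − 2 × 268.8)/2674 = 79.9% if all fall in the maintenance period. The mixed reading therefore shows a shortfall of about 10 points where the true one is about 20.

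**Sensitivity to day count.** With 673 days the literal score is 1346/2678 = 50.3%, unchanged to one decimal.

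**Dependence on exposure under the literal reading.** For a subject who misses nothing, the score is 2D / (14 + 4(D − 7)) at day D:
- Day 7: 14/14 = 100%.
- Day 28: 56/98 = 57.1%.
- Day 84: 168/322 = 52.2%.
- Day 336: 672/1330 = 50.5%.

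Early discontinuers would thus look more compliant than completers.

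**Capsules-taken summary.** Under the literal reading, the fully compliant completer is reported as having taken 1344 capsules instead of 2674.

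**Check of the correction.** Converting doses to capsules gives 7 × 2 × 1 + 665 × 2 × 2 = 2674, and 2674/2674 = 100%.

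**Reduced-dose periods.** Protocol 11.2.4 says: "Subjects who do not tolerate study treatment will reduce their dosage by taking 120 mg BID for up to 4 weeks". If capsules were counted against a fixed 4 per day, 28 such days would cost 28 × 2 = 56 capsules, and a subject who followed every instruction would score (2674 − 56)/2674 = 97.9%. This arises only with a capsule count. Under an expected-minus-missed rule nothing is deducted, because no dose was missed.

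**The case against.** The best defence is that the sentence is loosely worded and not wrong in intent. The displayed formula is capsules over capsules, the sentence names capsules as its result, and it says only that the total is calculated using doses. If the author meant capsules, and missed intake is also recorded in capsules, the figure is right for everyone. That reading is available, so a reader who infers that compliance will be wrong for every subject, or under any interpretation, goes further than the text allows. The mixed reading is also right for a subject who misses nothing. What remains is that the section never says so, and the protocol's own use of the word dose points to the literal reading.

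Three other inferences are tempting and not supported:
- **That this table is the only evidence of exposure.** SAP 5.2.5 summarises time on treatment net of temporary interruptions, and SAP 5.4.1 tabulates adverse events leading to interruption, dose reduction and discontinuation. These do not measure intake within treated time, but they are evidence of exposure.
- **That the SAP contradicts the protocol's capsule count.** Protocol 11.5 says how sites monitor compliance; it does not prescribe the SAP's numerator. Missed doses might be derived from that count or from the dosing case report form mentioned in Protocol 15.4.2. The documents do not say.
- **That days off drug are wrongly counted as expected.** SAP 5.2.6 uses days on study drug, and SAP 5.2.5 already excludes temporary interruptions from days on treatment. Only an explicit link is missing.

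**Conclusion.** The derivation is wrong as written and should be corrected, but the consequence is limited. Of three possible programs, one gives correct results, one scores a fully compliant 96-week subject at 50.3%, and one hides about half of non-adherence (89.9% shown where 80% is true). The 50.3% rests on the literal reading, on dose meaning one twice-daily administration as in Protocol 11.1, and on 672 days without reduction or interruption.

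Two descriptive outputs are affected: percent compliance and total capsules taken. In the visible text compliance does not define an analysis population (SAP 5.1) and does not enter the mixed models (SAP 5.3.1 and 5.3.2), so no primary or secondary estimate changes. The reduced-dose effect of 2.1 points is a secondary matter that depends on choosing a capsule count.

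**What to change.** Replace the last sentence of SAP 5.2.6 with a numerator stated in capsules. Either of two definitions works:

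1. Expected capsules minus the sum, over missed doses, of the capsules per dose on the day concerned.
2. Capsules dispensed minus capsules returned. This fits the count in Protocol 11.5 and the accountability records required by Protocol 12.1.4.

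State which data source supplies the missed doses or the counts. If option 2 is chosen, define expected capsules as the sum of the number prescribed on each day, so that reduced-dose periods the protocol allows are not scored as non-compliance. In either case, refer to SAP 5.2.5 for days on treatment, so that temporary interruptions are handled in the same way in both sections.

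The cost is one paragraph in the SAP and the matching program specification. It needs no new data if option 1 is used with missed doses already recorded, or option 2 with the accountability records already required.

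### SAP 5.2.6 puts the compliance denominator in capsules and the numerator in doses, with no conversion, although a maintenance dose is two capsules

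*SAP*

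**What the plan says.** SAP 5.2.6 (Treatment Compliance) plans to summarise the total capsules taken, compliance through the last dose, and 96-week compliance in subjects who complete the study. Percent compliance is capsules taken divided by capsules expected, times 100.

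- **Denominator (SAP 5.2.6).** Days on study drug are "multiplied by 4 (4 capsules is the expected number per day), except for the first week where 2 capsules a day is expected". This is a count of capsules.
- **Numerator (SAP 5.2.6, next sentence).** "The total number of capsules actually taken is calculated using total number of doses expected minus the missed doses". The result is called capsules, but both terms are doses.
- **Capsule strength (Protocol 12.1).** "Each capsule contains 120 mg BG00012".
- **Regimen (Protocol 11.1).** "BG00012 will be taken orally at a dose of 120 mg BID for the first 7 days and at a maintenance dose of 240 mg" twice daily from then on.
- **Meaning of a dose (Protocol 11.1).** In the missed-dose rule a dose is one intake: "If the subject does not remember to take the dose within 6 hours, this dose should be skipped".
- **How sites track compliance (Protocol 11.5).** "Compliance will be monitored by capsule count conducted by study personnel at protocol-scheduled visits".

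**The concern.** The numerator and denominator of one percentage are in different units, and from Day 8 those units differ by a factor of two. A programmer who follows the sentence must either divide doses by capsules or start from the expected capsules and take off a count of missed doses. Neither gives the share of capsules taken that the SAP's own formula calls for.

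What is at stake is the accuracy of two reported quantities, percent compliance and total capsules taken. Time on treatment (SAP 5.2.5) removes recorded interruptions but does not count individual missed doses. The 5.2.6 summary is therefore where a reader would look for missed drug in this single-arm study.

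**Working it through.** **Inputs.** Capsule 120 mg (Protocol 12.1). 120 mg twice daily for 7 days, then 240 mg twice daily, for 96 weeks = 672 days (Protocol 11.1). Assumed: no interruption and no dose reduction.

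**Reproducing the SAP's expected daily count.** Capsules per day = 2 × dose in mg / 120.
- Week 1: 2 × 120/120 = 2.
- Maintenance: 2 × 240/120 = 4.

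Both match SAP 5.2.6. The SAP's figure of 4 is thus itself two doses of two capsules.

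**Totals over 672 days.**
- Expected capsules C = 7 × 2 + 665 × 4 = 14 + 2660 = 2674.
- Expected doses = 672 × 2 = 1344, of which 665 × 2 = 1330 are maintenance doses.

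Let m be the number of missed maintenance doses.

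**Literal reading: (expected doses − m) / C.** With m = 0 the result is 1344/2674 = 50.3%, and total capsules taken is reported as 1344 instead of 2674. The ceiling depends on time on drug, because Week 1 doses are one capsule each:
- 4 weeks: 56/98 = 57.1%
- 12 weeks: 168/322 = 52.2%
- 48 weeks: 672/1330 = 50.5%
- Week 1 only: 14/14 = 100%

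**Mixed reading: (C − m) / C. Consistent units: (C − 2m) / C.**

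| Maintenance doses missed | m | Mixed reading | Consistent units |
|---|---|---|---|
| 10% | 133 | 2541/2674 = 95.0% | 2408/2674 = 90.1% |
| 20% | 266 | 2408/2674 = 90.1% | 2142/2674 = 80.1% |
| 50% | 665 | 2009/2674 = 75.1% | 1344/2674 = 50.3% |

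Under the mixed reading each missed maintenance dose removes one capsule instead of two, so missed maintenance drug is understated by exactly half. A missed Week 1 dose is one capsule and is counted correctly.

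**The case against.** The strongest defence is that the whole paragraph is about capsules: the ratio, the expected total, and the grammatical subject of the disputed sentence. On that view doses is a slip for capsules in both terms, the intended rule is expected capsules minus missed capsules, and the formula is right. This is possible and cannot be excluded. But the text does not say so, and Protocol 11.1 uses dose for an intake. The wording needs correcting even if the program turns out to be right.

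Three further objections stand, and they limit what can be claimed.

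- **A reader might infer that the report will show compliance near 50%.** That would be obvious in the output, since nobody treated for months would come near 100%, and it would probably be caught. The mixed reading is the one that could pass unnoticed.
- **A reader might infer that the lymphocyte results are affected, or that poor adherers will pass as acceptable.** The documents do not support this. The pharmacodynamic population requires one dose and one post-baseline measurement (SAP 5.1). The model terms are ALC subgroup, visit, baseline, age, gender and an interaction for the primary endpoints (SAP 5.3.1), and visit, baseline, age and gender for the secondary ones (SAP 5.3.2). No compliance threshold is set.
- **A reader might infer that the SAP abandons the protocol's capsule count.** SAP 5.2.6 does not say where missed doses come from. They may be derived from that count, or from the dosing CRF mentioned in Protocol 15.4.2, which is not available here.

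**Conclusion.** The point holds as an error of units in one sentence. Unless doses was loosely meant as capsules, the stated rule gives a wrong percent compliance and a wrong total of capsules taken. For an uninterrupted 96-week subject at full dose, the literal reading turns 100% into 50.3%. The mixed reading turns 90.1% into 95.0% and 80.1% into 90.1%. These figures assume that all missed doses fall in maintenance; the literal ceiling is higher for early discontinuers.

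The consequence is confined to the descriptive compliance summary. No visible endpoint analysis or population depends on it, so the priority is low.

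**What to change.** Replace the last sentence of SAP 5.2.6 with a rule in capsules, and state the data source. Either of these would do:

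1. Capsules taken = expected capsules minus missed capsules. Each missed dose is converted at the capsules per dose in force that day, that is, dose in mg / 120: 1 on any 120 mg twice-daily day, 2 on 240 mg twice-daily days. The 120 mg days include Week 1, the restart week in Protocol 11.2.2 and temporary reductions under Protocol 11.2.4.
2. Capsules taken from the Protocol 11.5 capsule count: dispensed minus returned, with lost or destroyed capsules also deducted. Protocol 12.1.4 requires records of these; dispensed minus returned alone would count them as taken.

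Under option 1, also state the expected count on reduced-dose days after Week 1, because the SAP counts 4 on every such day. For a 28-day reduction the difference is 28 × 2 = 56 capsules, or 56/2674 = 2.1% of the 96-week total. This is separate from the unit error but belongs in the same sentence.

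The cost is one SAP sentence and a small change to one derivation. Option 2 uses records the protocol already requires. Option 1 needs missed doses to be recorded so that the dose level on the day is known.
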